7. STATISTICAL ANALYSIS

Main study parameter/endpoint

Feasibility of ADD: 75% of included patients complete the intervention.

Other endpoints are descriptive.

8. ETHICAL CONSIDERATIONS

h. Regulation statement

The study will be conducted according to the principles of the Declaration of Helsinki and in accordance with the Medical Research Involving Human Subjects Act (WMO).

i. Recruitment and consent

Patients will be recruited by all pulmonologists, residents and respiratory nurses working in the Spaarne Gasthuis. The health care professional will inform the patient about the study, and will get their consent to give their information to the research. The researchers will send the patient a letter, in which the study is explained in detail. At least one week later, they will be called by a member of the ADD team who will answer any questions. If the patient is willing to participate, he or she signs the informed consent form at the first visit.

j. Benefits and risks assessment, group relatedness

The burden for participants is deemed acceptable. The patient receives an individual training tailored to his or her needs by experienced health care professionals. During the intervention, the patient has an important say in how further visits are planned. The intervention ends as soon as the patient feels that goals have been reached. This pilot study is an important step in the development of dyspnea services in the Netherlands. The investigator has shared the study protocol during a meeting with pulmonologists concerning palliative care for COPD (Sectie palliatieve zorg NVALT meeting on the 7th of February 2019). Other pulmonologists are interested to introduce this method in centers for COPD care.

k. Incentives (if applicable)

Participants will receive payment of travel expenses.

9. SAFETY REPORTING

9.1 Temporary halt for reasons of subject safety

In accordance to section 10, subsection 4, of the WMO, the sponsor will suspend the study if there is sufficient ground that continuation of the study will jeopardise subject health or safety. The sponsor will notify the accredited METC without undue delay of a temporary halt including the reason for such an action. The study will be suspended pending a further positive decision by the accredited METC. The investigator will take care that all subjects are kept informed.

9.2 AEs, SAEs and SUSARs

9.2.1 Adverse events (AEs)

Adverse events are defined as any undesirable experience occurring to a subject during the study, whether or not considered related to the intervention. All adverse events reported spontaneously by the subject or observed by the investigator or his staff will be recorded.

9.2.2 Serious adverse events (SAEs)

Due to the nature of this study, occurrence of SAEs is not possible.

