Rationale: In severe COPD, breathlessness is a distressing symptom which has a huge impact on quality of life. Management of breathlessness is complex and should comprise both pharmacological and non-pharmacological interventions, tailored to the individual needs of the patient and provided by a multidisciplinary team. Such 'breathlessness services' have been developed in recent years, mainly in the United Kingdom. In the Netherlands, these services do not yet exist in primary or secondary care.

Objectives:

To assess feasibility of a Dutch breathlessness service, and to evaluate patient satisfaction.

Study design: Single-centre, non-blinded mixed-methods, cohort feasibility study.

Study population: Patients with COPD (diagnosed by a pulmonologist,

postbronchodilatator FEV1/FVC below the lower limit of normal) and refractory dyspnea

(troubled by breathlessness in spite of optimization of COPD treatment) who are able to visit

the outpatient clinic.

Intervention:

The intervention will be delivered by a multidisciplinary team, formed by a pulmonologist, a physiotherapist with expertise in COPD, and 3 respiratory nurses. For every patient, an individual management plan will be developed, based on the Breathing Thinking Functioning-model (see main document for details). The main intervention is delivered by both the respiratory nurse and the physiotherapist, twice a week for two to six weeks. During these sessions, patients learn strategies to cope with their dyspnea in both a cognitive and functional manner. The pulmonologist will prescribe opioids and/or benzodiazepines if applicable.

Main study parameters/endpoints:

Feasibility: 75% of patients fullfills intervention

Nature and extent of the burden and risks associated with participation, benefit and group relatedness:

The only burden for participants will be the hospital visits. However, these visits will be minimised as much as possible by combining them with other hospital visits where possible. If visiting the hospital is too burdensome, home visits will be arranged.

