1. INTRODUCTION AND RATIONALE

Chronic Obstructive Pulmonary Disease (COPD) is a progressive disease causing about 7000 deaths in the Netherlands each year, thereby being the fourth leading cause of death (1). Studies have shown a high symptom burden in patients with end-stage COPD, at least similar to patients with incurable lung cancer (2). The main symptom is dyspnea, or breathlessness, which increases as disease progresses. It often results in emergency hospital admissions, which results in a high burden of disease on both patient, relatives and the health care system. Patients with COPD who experience refractory symptoms may be referred to a tertiary rehabilitation centre, where adequate patient education is provided including help with breathlessness, in an inpatient setting. However, patients with advanced respiratory failure are not always eligible for such programmes due to their instability, or they do not wish to be away from home for such a long period of time. Those patients are mostly dependent on their physiotherapist for breathlessness management. However, dyspnea is a complex symptom with cognitive and behavioural aspects. Most physiotherapists are not trained to address breathlessness in its full complexity.

In recent years, Booth and Spathis have developed the breathing-thinking-functioning model (BTF), which conceptualizes the three cognitive and behavioural reactions to dyspnea (3).

Breathing domain: Dyspnea causes dysfunctional breathing patterns with an increased respiratory rate and use of accessory muscles, leading to inefficient (dead space) ventilation. Furthermore, patients with COPD who feel breathless tend to focus on the in-breath instead of on the out-breath. This promotes dynamic hyperinflation which increases the breathlessness and the work of breathing. When addressing the breathing domain, patients learn adequate breathing techniques. Also, they will be given a hand-held fan. Growing evidence suggests that cool airflow from a fan can decrease breathlessness (13).

Thinking domain: misconceptions such as 'I will suffocate', but also memories of earlier episodes of dyspnea, lead to anxiety and distress in many patients. This leads to tachypnea which increases dyspnea. When addressing the thinking domain, patients learn that they may feel very breathless but will not suffocate. Also, they will learn how inadequate breathing techniques caused by anxiety influence their complaints.

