3. STUDY DESIGN

The intervention will be delivered by a multidisciplinary team, formed by a pulmonologist, a physiotherapist with expertise in COPD, and 3 respiratory nurses.

Prior to start of the study, physiotherapist and respiratory nurses receive ADD training by pulmonologist, who has received an BTF training in Cambridge.

Step 1: All pulmonologists, residents and respiratory nurses of the Spaarne Gasthuis recruit patients with COPD with refractory breathlessness who fullfill the inclusion critera (see chapter 4).

Step 2: Patients who are eligible are given an information letter by the recruiting health care professional, or the letter is sent to the patient by a member of the ADD team. After at least 7 days, they receive a call from a member of the ADD team, asking if they have any questions concerning the study and whether they want to participate.

Step 3: Assessment for eligibility by pulmonologist (if not eligible, this is noted in case record form); first appointment within one week.

Step 4: First appointment (approximately 1.5 hrs). Patient comes with key (informal) carer.

- Explanation of ADD by pulmonologist and nurse.
- Patient signs informed consent form
- Aided by nurse, patient fills in the CRQ.
- Informal caregiver gives NRS rating for distress due to patient's breathlessness
- Patient meets physiotherapist
- Current medication is reviewed by pulmonologist. Medication for symptom control is optimised if necessary (e.g., morphine for dyspnea).
- Patient receives ADD booklet with breathing exercises and relaxation exercises and a handheld fan, and explanation why this works (stimulation of the nervus vagus in the face)

Step 5: At the end of the first appointment, the customized intervention program is made together with the patient.

- 1. All patients will have at least one session with the physiotherapist. The maximum number of sessions is six (once every week).
- 2. All patients will have weekly contact with the respiratory nurse; at least two times in the hospital (combined with physiotherapist), other contacts may be by telephone. If it is too burdensome for patients to come to the hospital, they will receive a home visit. During these contacts, the nurse will go through the given information again, coach the patient, and assess whether the intervention is helpful for the patient.

Table 1)

	explanation	intervention	Intervention is given by
Breathing	Dysfunctional breathing	Breathing retraining directions	Physiotherapist

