4. STUDY POPULATION

Inclusion criteria

Base population: COPD patients who are treated in the outpatient clinic of the Spaarne Gasthuis.

In order to be eligible to participate in this study, a patient must meet all of the following criteria:

- COPD, diagnosed by a pulmonologist, with postbronchodilatator FEV1/FVC below the lower limit of normal
- refractory dyspnea (troubled by breathlessness in spite of optimization of COPD treatment, MRC dyspnea score at least 2 points). Since dyspnea is a symptom, there are no objective criteria, only questionnaires. As in other studies investigating dyspnea services and pulmonary rehabilitation, we use the MRC score for inclusion, which scores during which activity the patient becomes dyspnoic. A MRC dyspnea score of 2 points indicates dyspnea during hurrying or walking up a slight hill. Off note, this intervention is only offered to patients who complain of dyspnea in their daily life. Many COPD patients have an MRC dyspnea score of 2, but are not troubled by the symptom.
- able to visit the outpatient clinic
- able to read and understand the Dutch language
- mentally competent, as assessed by recruiting health care professional

Exclusion criteria

A potential patient who meets any of the following criteria will be excluded from participation in this study:

- An acute exacerbation of COPD, leading to hospitalisation, in 6 weeks before inclusion.
- An acute exacerbation during the study period, will lead to exclusion with the
 possibility to re-enter after stabilization. In that case, patients will follow the same
 study procedures again.
- Active participation in another trial

Sample size calculation

Number of subjects: 20.

Rationale: The primary aim of the present study is to assess feasibility of a new service in the Netherlands. This service is an adjusted variant of an existing service for which there is robust evidence. If ADD is feasible and effective in a pilot study population, we aim to conduct a larger randomised clinical trial regarding effectiveness. In that case, our power

C1onderzoeksprotocol2019.199versie4 dd 01-082019

Introductiondyspneaserviceversie4

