6. METHODS

c. Study parameters/endpoints

i. Main feasibility criteria:

75% of included patients complete the intervention.

ii. Secondary study parameters/endpoints

- 1. Description of components and practical aspects of ADD.
- 2. semi-structured interviews with patients and carers to evaluate ADD after six weeks.

d. Study procedures

Baseline	Completion of programme	
CRQ	CRQ	
NRS carer distress	NRS carer distress	
	Semi-structured interview with patient and informal caregiver regarding	
	intervention	
	Structured interviews with the ADD team regarding the intervention	

e. Withdrawal of individual subjects

Subjects can leave the study at any time for any reason if they wish to do so without any consequences.

i. Specific criteria for withdrawal (if applicable)

Hospitalisation for COPD exacerbation during study period. An acute exacerbation during the study period, will lead to exclusion with the possibility to re-enter after stabilization. In that case, patients will follow the same study procedures again.

f. Replacement of individual subjects after withdrawal

After withdrawal, a new subject will be included in the study.

g. Follow-up of subjects withdrawn from treatment

Withdrawal will be recorded in the case record form. Patients will be approached to re-enter the study after stabilisation in case of COPD exacerbation. In that case, they re-start the programme.

082019 15 of 22

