10.3 Annual progress report

The sponsor/investigator will submit a summary of the progress of the trial to the accredited METC once a year. Information will be provided on the date of inclusion of the first subject, numbers of subjects included and numbers of subjects that have completed the trial, serious adverse events/ serious adverse reactions, other problems, and amendments.

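### Section 9.2.2 rules out serious adverse events that the protocol elsewhere foresees, so none could be classified, promptly reported or followed up as serious

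*Protocol*

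**What the plan says.** Section 9.2.2 consists of one sentence: "Due to the nature of this study, occurrence of SAEs is not possible". Sections 9.2.3 to 9.2.5 (SUSARs, annual safety report, follow-up of adverse events) are each marked as not applying.

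Other parts of the protocol bear on the same question:

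- **Section 9.2.1** sets the scope of adverse events: "Adverse events are defined as any undesirable experience occurring to a subject during the study, whether or not considered related to the intervention". It then requires that all events which the subject reports spontaneously, or which the study staff observe, be recorded.
- **Section 6e** gives as a specific withdrawal criterion "Hospitalisation for COPD exacerbation during study period". Section 6f replaces withdrawn subjects. Section 6g records the withdrawal in the case record form and has patients approached for re-entry once stable.
- **Section 4** plans for the same situation: "An acute exacerbation during the study period, will lead to exclusion with the" possibility of re-entry.
- **Section 1** says of dyspnea in COPD: "It often results in emergency hospital admissions".
- **Summary, Intervention**: "The pulmonologist will prescribe opioids and/or benzodiazepines if applicable". Section 3, Step 4, has the pulmonologist review medication at the first visit and optimise symptom control if needed, with morphine as the example.
- **Section 10.3** lists "serious adverse events/ serious adverse reactions" among the items in the yearly report to the METC.

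**The concern.** The reason given in 9.2.2 is the nature of the study, which presumably means that a coaching and breathing programme is low-risk. That would be an argument about events caused by the intervention. Section 9.2.1 sets relatedness aside, so a low-risk intervention cannot make serious events impossible. They can arise from the disease alone, and the protocol names one that it expects to have to handle.

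The safety record of the pilot is at stake. The study is meant to prepare a multi-hospital randomised trial. If no event can be called serious, a statement that no SAEs occurred would follow from the wording of 9.2.2 and not from observation. A reader of the pilot report, or the METC reading the annual report, could not tell the two apart.

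**Working it through.** **Step 1: the texts side by side.** The protocol states no figure on this point, so there is none to reproduce. The check is textual.

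| Place | What it implies about serious events |
|---|---|
| 9.2.2 | They cannot occur |
| 6e | Hospitalisation for exacerbation is foreseen and leads to withdrawal |
| 4 | Exacerbation during the study is foreseen |
| 1 | Emergency admission is frequent in this disease |
| 9.2.1 | Events count regardless of cause |
| Summary; 3, Step 4 | The study team may prescribe opioids and/or benzodiazepines, conditionally |
| 10.3 | SAEs are to be reported yearly to the METC |

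One outside premise is needed: that hospitalisation makes an event serious. This is part of the general SAE definition, which the protocol does not print. With that premise, 6e and 9.2.1 together contradict 9.2.2. Section 10.3 contradicts it without any premise, because it promises information on a category that 9.2.2 declares empty.

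**Step 2: what happens to a hospitalised patient if the text is followed.**

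1. The event is recorded as an adverse event if reported or observed (9.2.1).
2. The withdrawal is entered in the case record form (6g), and a new subject is included (6f).
3. Nothing directs anyone to judge seriousness, since 9.2.2 offers no definition.
4. Nothing sets a prompt route or a time limit for reporting a serious event. Section 10.3 is yearly.
5. Nothing directs follow-up of the event, since 9.2.5 is marked as not applying.

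The event therefore leaves a trace, but not as a serious one.

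**Step 3: illustration of size.** The planned number is 20 (section 4). The protocol gives no hospitalisation rate, so the risk p per patient over the six weeks is an assumption, taken from 1% to 15%. Treating patients as independent:

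- expected number of patients with an event = 20 × p
- chance of at least one = 1 − (1 − p)^20

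| Assumed p | Expected | Chance of at least one |
|---|---|---|
| 1% | 0.2 | 1 − 0.99^20 = 18% |
| 2% | 0.4 | 1 − 0.98^20 = 33% |
| 5% | 1.0 | 1 − 0.95^20 = 64% |
| 10% | 2.0 | 1 − 0.90^20 = 88% |
| 15% | 3.0 | 1 − 0.85^20 = 96% |

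The claim of impossibility is not supported anywhere in this range. Because withdrawn subjects are replaced, the number actually included may exceed 20, which would raise these chances slightly.

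**The case against.** The best defence is that the protocol does capture these events. Section 9.2.1 requires recording of every reported or observed adverse event, related or not. Section 6g records withdrawals and implies some later contact, since patients are approached again after stabilisation. Section 10.3 names SAEs and also other problems. All of this stands. A reader might infer that serious events would go unrecorded or never reach the METC, and the documents do not support that reading. The gap is in classification, prompt reporting and follow-up.

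A reader might also infer that the sponsor would lack the information needed for the temporary halt in section 9.1. That does not follow. The halt is not tied to an SAE count, and a small single-centre team would hold the recorded events, though without a seriousness label. Nor does the protocol say how a death during the study would be handled, so nothing here rests on that.

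Three further points are fair. Prescribing is conditional, and benzodiazepines appear only in the summary. Section 4 excludes patients hospitalised for an exacerbation in the six weeks before inclusion, which may lower the rate. The primary endpoint is completion, so its definition, the sample size and its analysis do not depend on this section. These points lower the expected number of events or limit the consequence. None of them makes a serious event impossible.

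**Conclusion.** Section 9.2.2 is wrong as written; this is more than a missing detail. It conflicts with sections 1, 4, 6e, 9.2.1 and 10.3, and it is hard to square with the conditional prescribing in the summary and section 3. The consequence is bounded: events would be recorded as ordinary adverse events or withdrawals, but none could be classified as serious, reported promptly as such, or followed up, and the pilot could report zero SAEs by definition.

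The conclusion rests on the text and on the general convention that hospitalisation is serious. It does not depend on the rates in the table, which are assumptions. They show only that one or more such events in 20 patients is plausible: about one chance in five at a 1% risk, and more likely than not at 5%.

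**What to change.** 1. Delete the impossibility statement in 9.2.2. Replace it with a standard SAE definition that applies whether or not the event is related to the intervention.
2. Add a reporting route to the METC with its timelines, covering consent to the final visit and including patients withdrawn for an exacerbation. Foreseen COPD hospitalisations may go on a line listing, to keep the workload proportionate.
3. In 9.2.5, provide for follow-up of adverse events in place of the present entry.
4. In the study report, give the number and proportion of patients with an SAE among all included patients, including those later replaced.
5. Check that sections 9.2.3 and 9.2.4 and the yearly report in 10.3 agree with the new text.

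This changes safety reporting only and touches no treatment or withdrawal rule. The cost is a protocol amendment and a short SAE form.

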9.2.3 Suspected unexpected serious adverse reactions (SUSARs)

Not applicable.

9.2.4 Annual safety report

Not applicable.

9.2.5 Follow-up of adverse events

Not applicable.

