5. TREATMENT OF SUBJECTS

a. Investigational product/treatment

See table 1 in section 3.

b. Use of co-intervention (if applicable)

Study subjects continue using their usual medication.

If medication is adjusted or added by the ADD team, this is noted in the case report form.

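### Section 9.2.5 declares adverse-event follow-up inapplicable, although the team may start or change opioids or benzodiazepines, so a recorded side effect has no planned study follow-up (minor)

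*Protocol*

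**What the plan says.** On medication, the Protocol speaks in four places.

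- The summary, under the intervention: "The pulmonologist will prescribe opioids and/or benzodiazepines if applicable".
- Section 3, Step 4, first appointment: "Medication for symptom control is optimised if necessary (e.g., morphine for dyspnea").
- Section 3, Table 1: medication appears in the breathing domain, with the pulmonologist as provider.
- Section 5b, under co-intervention: "If medication is adjusted or added by the ADD team, this is noted in the case report form".

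On adverse events, section 9.2.1 defines them broadly, without regard to whether the intervention caused them, and adds: "All adverse events reported spontaneously by the subject or observed by the investigator or his staff will be recorded". The section headed "9.2.5 Follow-up of adverse events" reads in full: "Not applicable".

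**The concern.** Declaring follow-up inapplicable would suit a programme made up only of breathing exercises, coaching and advice. This programme also allows the team's pulmonologist to start or change sedating drugs, in patients whom section 2 describes as elderly and multimorbid. Side effects of those drugs are adverse events under the protocol's own definition.

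At stake is a limited matter of patient safety and of what the pilot can report. The study would record that a side effect occurred but has no plan to establish whether it resolved. That outcome would be useful to know before the phase III trial that the pilot is meant to prepare.

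**Working it through.** No arithmetic applies, and the plan gives no figure on this point. The check is whether the entry in 9.2.5 fits the rest of the protocol, and whether another section supplies what it leaves out.

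**Step 1. Can the study team cause a drug side effect?** Yes. The summary, Step 4, Table 1 and section 5b all allow it. Benzodiazepines are named only in the summary. Morphine in Step 4 is enough to make the point from the body of the protocol alone.

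**Step 2. Would such a side effect be recorded?** Yes, if the patient reports it or staff observe it (9.2.1).

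**Step 3. Does any other section provide follow-up of that event?**

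| Place in the Protocol | What it provides | Follow-up of one patient's event? |
|---|---|---|
| Section 3, Step 5 | Weekly nurse contact to repeat information, coach, and judge whether the programme helps | Not stated; side effects are not named |
| Section 3, Step 6 | Final visit with CRQ, carer distress rating and an interview about experiences | Not stated |
| Section 6g | Withdrawal is noted in the case record form; "Patients will be approached to re-enter the study after stabilisation in case of COPD exacerbation" | No; this concerns recording of withdrawal and re-entry |
| Section 9.1 | "the sponsor will suspend the study if there is sufficient ground that continuation of the study will jeopardise subject health or safety" | No; this acts on the whole study |
| Section 9.2.2 | Serious events are declared impossible | No; no serious-event route supplies follow-up |

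**Step 4. Is this a matter for the SAP?** No. Follow-up of adverse events belongs in the protocol, and here the protocol has a section for it and expressly sets it aside.

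**Result.** The protocol plans to record these events and declares their follow-up inapplicable. No other section closes the gap.

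**The case against.** The best case for leaving the text alone is that little follows from it. Participants are existing outpatients of the hospital, a pulmonologist reviews their medication, and section 5b treats drug changes as co-intervention. All patients have weekly nurse contact, with home visits where needed, and a final visit with an interview. A drug that a patient tolerates badly would plausibly come up on one of these occasions, and 9.2.1 would then have it recorded. What is left is that the outcome of an event may be missing from the case report form of a 20-patient, single-arm feasibility study.

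Much of this stands, and it sets the ceiling at minor. It does not remove the point. These contacts could reveal a side effect, but nothing directs staff to ask about one or to return to one already recorded.

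A reader might infer more than the text supports:

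- **That side effects would go unmanaged.** The entry in 9.2.5 concerns study follow-up. It does not bar ordinary clinical care.
- **That early finishers face a measurable interval without contact.** The summary lets the main programme end after two weeks and the final visit comes after six, but the two-week minimum stands only in the summary. Step 5 promises weekly nurse contact without saying whether it stops when the programme does. This is an ambiguity and does not measure the gap. The gap is a missing rule for all recorded events.
- **That patients are not properly told about drug risks.** That is a separate question of disclosure. It cannot be judged here, because the consent pages are not among the documents.

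**Conclusion.** The point holds, as a minor one. Section 9.2.5 sets aside follow-up in a study whose team may start or change opioids and/or benzodiazepines and must record the side effects it learns of.

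Its size cannot be put in numbers. Prescribing is conditional and the protocol gives no expected share of the 20 planned patients. One patient started on morphine would be enough to make follow-up applicable. The primary endpoint, completion of the intervention by 75% of included patients, and the way it is counted are unaffected.

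The verdict assumes that the medication wording means what it says, so that the team may prescribe during the study. It also assumes that no follow-up rule stands in a study document that is not shown.

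**What to change.** Replace the entry in 9.2.5 with a rule along these lines:

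- Recorded adverse events are followed until resolution or stabilisation, or until the six-week final visit. If an event is still open at that visit, its status is recorded and it is handed to the treating pulmonologist.
- In patients whose medication the ADD team started or changed, the nurse asks about side effects at the existing weekly contacts.
- Patients who finish early or withdraw with an unresolved event are telephoned at the six-week point, if they agree.

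The last item is needed because a withdrawn patient may have no final visit, and because section 6d ties the closing assessments to completion of the programme while Step 6 places them after six weeks.

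The cost is a short protocol amendment, which needs the ethics committee's favourable opinion under section 10.2, slightly more adverse-event recording and an occasional telephone call. No visit is added, and neither the sample size nor the primary endpoint changes.
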